7. SAFETY MONITORING AND REPORTING

7.1 Definitions

7.1.1. Adverse Event (AE)

An adverse event is any untoward medical experience or change of an existing condition that occurs during or after treatment, whether or not it is considered to be related to the protocol intervention.

7.1.1.1 Serious Adverse Event (SAE)

A serious adverse event is any expected or unexpected adverse events that result in any of the following outcomes:

- Death
- Is life-threatening experience (places the subject at immediate risk of death from the event as it occurred)
- Unplanned hospitalization (equal to or greater than 24 hours) or prolongation of existing hospitalization
- A persistent or significant disability/incapacity
- A congenital anomaly/birth defect
- Secondary malignancy*
- Any other adverse event that, based upon appropriate medical judgment, may jeopardize the subject's health and may require medical or surgical intervention to prevent one of the outcomes listed above (examples of such events include allergic bronchospasm requiring intensive treatment in the emergency room or at home, blood dyscrasias or convulsions that do not result in inpatient hospitalization, or the development of drug dependency or drug abuse).

*Modified from [21 CFR 312.32](#)

7.1.1.2 Unanticipated Problems Involving Risks to Subjects or Others

An unanticipated problem is any incident, experience, or outcome that **meets all three** of the following criteria:

1. Unexpected (in terms of nature, severity, or frequency) given the following: a) the research procedures described in the protocol-related documents such as the IRB approved research protocol, informed consent document or Investigator Brochure (IB); and b) the characteristics of the subject population being studied; **AND**
2. Related or possibly related to participation in the research (possibly related means there is a reasonable possibility that the incident, experience, or outcomes may have been caused by the drugs, devices or procedures involved in the research); **AND**
3. Suggests that the research places subjects or others at greater risk of harm (including physical, psychological, economic, or social harm) than previously known or recognized.

7.1.1.3 Adverse Events of Special Interest (AESI)

Specific adverse events, or groups of adverse events, will be followed as part of standard safety monitoring activities. These events, regardless of seriousness, will be reported.

7.1.2 Assessment of Adverse Events

The site Investigator will be responsible for determining the event name, assessing the severity (i.e. grade), expectedness, and attribution of all adverse events.

7.1.2.1 Assessment of Adverse Event Name and Grade

Adverse events will be characterized using the descriptions and grading scales found in **The NCI Common Terminology Criteria for Adverse Events (CTCAE) v. 4.0**. A copy of the scale can be found at [the NCI/CTEP web site](#). The determination of severity for all other events not listed in the **CTCAE** should be made by the investigator based on medical judgment and the severity categories of Grade 1 to 5 as defined below:

- Grade 1 (mild) – An event that is usually transient and may require only minimal treatment or therapeutic intervention. The event does not generally interfere with usual activities of daily living.
- Grade 2 (moderate) – An event that is usually alleviated with additional specific therapeutic intervention. The event interferes with usual activities of daily living, causing discomfort but poses no significant or permanent risk of harm to the subject.
- Grade 3 (severe) – An event that requires intensive therapeutic intervention. The event interrupts usual activities of daily living, or significantly affects the clinical status of the subject.
- Grade 4 (life threatening) – An event, and/or its immediate sequelae, that is associated with an imminent risk of death or with physical or mental disabilities that affect or limit the ability of the subject to perform activities of daily living (eating, ambulation, toileting, etc).
- Grade 5 (fatal) – Death (loss of life) as a result of an event.

7.1.2.2 Assessment of Attribution

The following definitions will be used to determine the causality (attribution) of the event to the study agent or study procedure.

- **Unrelated** – The event is clearly related to other factors such as the participant's clinical state, other therapeutic interventions, or concomitant medications administered to the participant.
- **Unlikely** – The event is doubtfully related to the investigational agent(s). The event was most likely related to other factors such as the participant's clinical state, other therapeutic interventions, or concomitant drugs.
- **Possible** – The event follows a reasonable temporal sequence from the time of drug administration, but could have been produced by other factors such as the participant's clinical state, other therapeutic interventions, or concomitant drugs.
- **Probable** – The event follows a reasonable temporal sequence from the time of drug administration, and follows a known response pattern to the study drug. The event cannot be reasonably explained by other factors such as the participant's clinical state, therapeutic interventions, or concomitant drugs.
- **Definite** – The event follows a reasonable temporal sequence from the time of drug administration, follows a known response pattern to the study drug, cannot be reasonably explained by other factors such as the participant's condition, therapeutic interventions, or concomitant drugs, AND occurs immediately following study drug administration, improves upon stopping the drug, or reappears on re-exposure.

7.1.2.3 Assessment of Expectedness

The following definitions will be used to determine the expectedness of the event:

- **Unexpected** – An adverse event is unexpected if it is not listed in the investigator's brochure and/or package insert; is not listed at the specificity or severity that has been observed; is not consistent with the risk information described in the protocol and/or consent; is not an expected natural progression of any underlying disease, disorder, condition, or predisposed risk factor of the research participant experiencing the adverse event. *Modified from [21 CFR 312.32 \(a\)](#)
- **Expected** – An adverse event is expected if it does not meet the criteria for an unexpected event, OR is an expected natural progression of any underlying disease, disorder, condition, or predisposed risk factor of the research participant experiencing the adverse event.

7.1.3 Reporting of Adverse Events

7.1.3.1 Routine Reporting of Non-Serious Adverse Events by Site Investigators

Routine AE recording will occur via data entry into the study eCRF. Recording of adverse events will begin once the patient is consented and will continue until **30 days after the patient's last dose**. Adverse events will be monitored by the Protocol Management Team (PMT). Adverse events that do not meet the criteria of serious OR are not unanticipated problems do not require expedited reporting. AEs reported through expedited processes (i.e. reported to the IRB, DSMC, FDA, etc.) must also be reported in routine study data submissions.

7.1.3.2 Expediting Reporting Requirements of SAEs and UPs by Site Investigators

7.1.3.2.1 Criteria for Reporting SAEs/UPs to the Coordinating Center

Serious Adverse Events meeting the criteria specified below will be reported to the Coordinating Center within **24 hours** of notification that the event occurred.

Adverse events that require expedited reporting include:

- AEs or SAEs that meet the definition of an unanticipated problem
- All deaths that occur within 30 days of active treatment
- All deaths that occur after 30 days of active treatment that are unexpected and possibly, probably, or definitely related to the study agent or procedure
- All serious adverse events, regardless of relationship to study agent or study procedure, that occur within 30 days of the last day of treatment
- All serious adverse events that occurred after 30 days of active treatment/therapy that are considered possibly, probably, or definitely related to the study agent or procedure

Note: Follow-up reports must be submitted for all events that require expedited reporting when the status of the event changes and until the resolution or stabilization of the event.

Reportable serious adverse events must be followed until the event is resolved, stabilized, or determined to be irreversible by the participating investigator; for ongoing reportable adverse events that are unrelated to study agent, the follow-up period may end at the 30-days post study-drug assessment. The Coordinating Center should be consulted prior to ending the follow-up of events that have stabilized.

7.1.3.2.2 Non-COH Sites: Procedure for Reporting SAEs/UPs to the COH Data Coordinating Center

1. Sites are to report to their local IRB per their site's specific institutional and IRB guidelines. As soon as possible, non-COH sites will provide to the COH Data Coordinating Center copies of the IRB submission and corresponding IRB response.
2. Document/describe the SAE/UP on each of the following:
 - a. MedWatch 3500A
 - i. Downloadable form at <http://www.fda.gov/medwatch/getforms.htm>
 - b. UP/SAE Coversheet
 - i. SAE Coversheet is found in Appendix **[J]**. A modifiable Microsoft Word document is also available from the Data Coordinating Center. An electronic signature on the document will be accepted.
3. Scan and email above documents to [contact] with the subject title as "IRB # SAE".
 - a. All SAE reports received at this account are forwarded immediately to study Principal Investigator, and to Coordinating Center personnel.
 - b. While not required, if available and applicable, please also include the local IRB submission for this event in the submission.
4. If an email receipt from Coordinating Center personnel is not received within one working day, please call [contact] [name] and/or email [contact].

7.1.3.2.3 COH Investigative Sites: Procedure for Reporting SAEs/UPs to the Coordinating Center

1. Email the following information to [contact] and [contact].
 - a. Participant ID, date the event met criteria for reporting, whether the event meets the definition of serious, whether the event is an unanticipated problem, grade of event, attribution of event, whether the event is a known expected toxicity to study agent.
2. Complete the iRIS AE/UP reporting form per COH reporting timeline.

7.1.3.3 Additional Reporting Requirements of the Study Principal Investigator

7.1.3.3.1 Reporting to COH IRB and DSMC

The study PI (or designee) will report to COH IRB and DSMC via [iRIS](#) all reportable serious adverse events that occur at COH and non-COH sites and meet COH IRB and DSMC expedited reporting criteria according to [City of Hope's Institutional policy](#). The study PI will also submit a Protocol Management Team (PMT) report to the COH DSMC at the frequency outlined in Section 3.6. This report will include a review of aggregate adverse event data.

7.1.3.3.2 Reporting to the FDA

Serious Adverse Events meeting the requirements for expedited reporting to the Food and Drug Administration (FDA), as defined in [21 CFR 312.32](#), will be reported as an IND safety report using the [MedWatch Form FDA 3500A for Mandatory Reporting](#).

The criteria that require reporting using the Medwatch 3500A are:

- Any unexpected fatal or life threatening adverse experience associated with use of the drug must be reported to the FDA no later than 7 calendar days after initial receipt of the information [\[21 CFR 312.32\(c\)\(2\)\]](#)
- Any adverse experience associated with use of the drug that is both serious and unexpected must be submitted no later than 15 calendar days after initial receipt of the information [\[21 CFR 312.32\(c\)\(1\)\]](#)
- Any follow-up information to a study report shall be reported as soon as the relevant information becomes available. [\[21 CFR 312.32\(d\)\(3\)\]](#)

7.1.3.3.3 Reporting to Participating Investigators

The study PI (or designee) will report all reportable serious adverse events to participating investigators as an IND Safety Report occurring within 30 calendar days of receipt of sponsor (lead site) notification, and indicate whether or not a protocol and/or consent form change is required. A cover letter will indicate the protocol title, the IND#, whether the FDA was informed, and, for non-COH sites, a statement that the report should be submitted to their local IRB for review as an IND safety report if applicable per local IRB policy.

The study PI will also forward to participating sites all IND safety reports received from **Novartis**, indicating whether a consent form or protocol change is required within 30 days of notification to study PI.

7.1.3.3.4 Reporting to Novartis

All serious adverse events and AESIs (initial and follow-up information) will be reported by the study PI to Novartis within 24 hours of learning of its occurrence per the following guidelines: Novartis Adverse Event Reporting Guidelines (section 7.1).

7.2.0 PROTOCOL DEVIATIONS AND SINGLE SUBJECT EXCEPTIONS

It is understood that deviations from the protocol should be avoided, except when necessary to eliminate an immediate hazard to a research participant. Brief interruptions and delays may occasionally be required because of travel delays, airport closures, inclement weather, family responsibilities, security alerts, government holidays, and so forth. Delays can also extend to complications of disease or unrelated medical illnesses not related to disease progression. The PI has the discretion to deviate from the protocol when necessary so long as such a deviation does not threaten patient safety or protocol scientific integrity. As a result of deviations, corrective actions are to be developed by the study staff and implemented promptly.

7.2.1 Definitions

7.2.1.1 Deviation

A deviation is a divergence from a specific element of a protocol that occurred without prior IRB approval. Investigators may deviate from the protocol to eliminate immediate hazard(s) for the protection, safety, and well-being of the study subjects without prior IRB approval.

Examples include, but are not limited to: a) dose adjustments based on excessive patient weight; b) alteration in treatment schedule due to non-availability of the research participant for treatment; and c) laboratory test results which are slightly outside the protocol requirements but at levels that do not affect participant safety.

7.2.1.2 Single Subject Exceptions (SSE)

An SSE is a planned deviation, meaning that it involves circumstances in which the specific procedures called for in a protocol are not in the best interests of a specific patient. It is a deviation that is anticipated and receives prior approval by the PI and the IRB.

7.2.2 Reporting of Deviations and SSEs

7.2.2.1 Reporting Deviations

For any deviation, the Investigator will notify the COH DSMC and IRB within 5 calendar days of its occurrence via iRIS in accordance with the Clinical Research Protocol Deviation policy.

A list of deviations from all participating sites will be submitted along with the Protocol Management Team (PMT) progress report to the COH DSMC.

For non-COH sites:

- The local IRB and/or DSMC must be notified according to local institutional policies.

- The study Principal Investigator must be notified as soon as practical (within 24 hours of notification of the event) via email to [contact] and [contact]. This email should provide input on the following:
 - Description of the event
 - Impact on participant safety or the safety to others
 - Impact on the study design
 - A corrective and preventative action plan

7.2.2.2 Reporting Single Subject Exceptions

The SSE must be submitted as a “Single Subject Exception Amendment Request” via [iRIS](#) in accordance with IRB guidelines and the [Clinical Research Protocol Deviation policy](#). An IRB approved SSE does not need to be submitted as a deviation to the DSMC.

All non-emergency planned deviations from the protocol must have **prior** approval by the Study Principal Investigator, the Site Principal Investigator, COH IRB, and when applicable, the local IRB. In addition, if contractually obligated, the sponsor must also approve the deviation.

7.3.0 STUDY OVERSIGHT, QUALITY ASSURANCE, AND DATA & SAFETY MONITORING

7.3.1 All Investigator Responsibilities

An investigator is responsible for ensuring that an investigation is conducted according to the signed investigator statement, the investigational plan, and applicable regulations; for protecting the rights, safety, and welfare of subjects under the investigator's care; and for the control of drugs under investigation.

All Investigators agree to:

- Conduct the study in accordance with the protocol and only make changes after notifying the Sponsor (or designee), except when necessary to protect the safety, rights or welfare of subjects.
- Personally conduct or supervise the study (or investigation).
- Ensure that the requirements relating to obtaining informed consent and IRB review and approval meet federal guidelines, as stated in § 21 CFR, parts 50 and 56.
- Report to the Sponsor or designee any AEs that occur in the course of the study, in accordance with §21 CFR 312.64.
- Ensure that all associates, colleagues and employees assisting in the conduct of the study are informed about their obligations in meeting the above commitments.
- Maintain adequate and accurate records in accordance with §21 CFR 312.62 and to make those records available for inspection with the Sponsor (or designee).
- Ensure that an IRB that complies with the requirements of §21 CFR part 56 will be responsible for initial and continuing review and approval of the clinical study.

- Promptly report to the IRB and the Sponsor all changes in the research activity and all unanticipated problems involving risks to subjects or others (to include amendments and IND safety reports).
- Seek IRB and Sponsor approval before any changes are made in the research study, except when necessary to eliminate hazards to the patients/subjects.
- Comply with all other requirements regarding the obligations of clinical investigators and all other pertinent requirements listed in § 21 CFR part 312.

7.3.2 Study Principal Investigator Responsibilities

The Study Principal Investigator is responsible for the conduct of the clinical trial, including overseeing that sponsor responsibilities as defined in § 21 CFR 312. Subpart D are executed in accordance with federal regulations.

7.3.3 Protocol Management Team (PMT)

The Protocol Management Team (PMT), minimally consisting of the study PI, site investigators, collaborating investigators, research nurse, clinical research associate/coordinator, and the study biostatistician, is responsible for ongoing monitoring of the data and safety of this study, including implementation of the stopping rules for safety/toxicity.

The PMT is recommended to meet (in person or via teleconference) at least monthly to review study status. This review will include, but not be limited to, reportable AEs and UPs, and an update of the ongoing study summary that describes study progress in terms of the study schema. The meeting will be a forum to discuss study related issues including accrual, SAE/AEs experienced, study response, deviations/violations and study management issues. The appropriateness of further subject enrollment and the specific intervention for subsequent subject enrollment are addressed. It is recommended that minutes of these discussions be taken to document the date of these meetings, attendees and the issues that were discussed (in a general format).

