7.3.6 City of Hope Data and Safety Monitoring Committee

This is a risk level 3 study as defined in the [City of Hope Institutional Data and Safety Monitoring Plan](#). This determination was made because this study is a Phase IIA trial that is IND Exempt.

The DSMC is a multidisciplinary committee charged with overseeing the monitoring of safety of participants in clinical trials, and the conduct, progress, validity, and integrity of the data for all clinical trials that are sponsored by City of Hope. The committee is composed of clinical specialists with experience in oncology and who have no direct relationship with the study. The committee reviews the progress and safety of all active research protocols that are not monitored by another safety and data monitoring committee or board.

The Study Principal Investigator is required to submit periodic status reports (the PMT report) according to the guidelines outlined in the [City of Hope Institutional Data and Safety Monitoring Plan](#). The PMT report will be submitted to the COH DSMC **every six months** from the date of activation.

The COH Data and Safety Monitoring Committee (DSMC) will review and monitor toxicity and accrual data from this trial. The DSMC will review up-to-date participant accrual; summary of all adverse events captured via routine and expedited reporting; a summary of deviations; any response information; monitoring reports, and summary comments provided by the study team. Other information (e.g. scans, laboratory values) will be provided upon request. For Phase I studies, a Phase I Tracking Log will be utilized and reviewed by the DSMC to monitor data and safety for dose escalation. A review of outcome results (response, toxicity and adverse events) and factors external to the study (such as scientific or therapeutic developments) is discussed, and the Committee votes on the status of each study.

Information that raises any questions about participant safety will be addressed with the Principal Investigator, statistician and study team. The PMT report and DSMC recommendations will be circulated to all participating sites for submission to their IRBs, in accordance with NIH guidance.

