13 STATISTICAL CONSIDERATIONS

13.1 Study Design

This study will be an open label, single arm, Phase IIA safety and tolerability study to describe the toxicity profile of ribociclib in combination with an aromatase inhibitor in patients aged 70 and older with hormone receptor positive metastatic breast cancer. We plan to study 40 evaluable participants. Participants that receive one dose of treatment will be considered evaluable, anyone that does not receive treatment will be replaced. We plan to stratify based on age such that at least 20 participants are aged 75 years or older. There will be one interim analysis after 20 participants have completed one cycle of the drug.

13.1.1 Primary Objective:

To estimate the safety and tolerability of the combination of ribociclib and an aromatase inhibitor in adults age 70 or older with hormone receptor positive metastatic breast cancer

13.1.2 Secondary Objectives:

1. To describe the full toxicity profile including all grades
2. To estimate the rate of worst grades of myelosuppression (neutropenia, leukopenia, thrombocytopenia, and anemia), neutropenic fever, GI side effects (nausea, diarrhea, decreased appetite, vomiting, stomatitis), fatigue, neuropathy, and thromboembolism
3. To describe rates of dose reductions, dose holds, and hospitalizations
4. To estimate objective response rate and clinical benefit rate as defined by modified RECIST (1.1) criteria
5. To estimate median progression-free and overall survival
6. To determine average plasma steady-state ribociclib C_{trough} concentrations in patients over the age of 70 years

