13.2 Sample Size and Accrual Rate

Given a sample size of 40 evaluable subjects the half-width of the 95% confidence limits for the rate of grade 2 or higher toxicities will be less than or equal to 0.16. For example if we saw a toxicity rate of 0.5 (20 subjects/40) the 95% lower and upper confidence limits would be 0.34 and 0.66, respectively. Further a sample size of 40 will allow us to see a toxicity with a true rate equal to 0.05 in 87 out of 100 trials.

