13.3 Interim Analyses

After approximately 20 subjects have completed at least one full cycle of treatment, the study team will review the data (including the toxicity profile, rates of dose reduction, holds and hospitalizations) and assess if the dose being studied is too high, requiring too many patients, in the opinion of the team, to experience a dose reduction. If so, a reduction of the dose will be considered, otherwise the study will continue to completion at the planned dose.

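### Section 7.3.3 has the management team implement stopping rules for toxicity, but the protocol text defines none, so no event count triggers a pause in accrual

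*Combined protocol and SAP*

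**What the plan says.** Section 7.3.3 lists the PMT's monitoring duties as "including implementation of the stopping rules for safety/toxicity" among others. It gives no cross-reference to where such rules are written. The same section describes the PMT's routine work: "The PMT is recommended to meet (in person or via teleconference) at least monthly to review study status". Whether further enrolment is appropriate is one of the topics for those meetings.

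The statistical section has one formal look. Section 13.1 states: "There will be one interim analysis after 20 participants have completed one cycle of the drug". Section 13.3 repeats it: "After approximately 20 subjects have completed at least one full cycle of treatment, the study team will review the data". The data reviewed include the toxicity profile and rates of dose reductions, holds and hospitalizations. The decision test is whether the dose is too high, "requiring too many patients, in the opinion of the team, to experience a dose reduction". The outcomes are: "If so, a reduction of the dose will be considered, otherwise the study will continue to completion at the planned dose". The synopsis says the same.

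Section 7.3.6 adds independent oversight: "The COH Data and Safety Monitoring Committee (DSMC) will review and monitor toxicity and accrual data from this trial". The PMT report goes to the DSMC every six months, and the committee votes on the study's status. No threshold is given.

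**The concern.** Section 7.3.3 relies on a safeguard that the protocol does not supply. A PMT following the text has no event definition, count or rate to apply.

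Section 13.3 cannot fill the gap. It gives no number, and neither listed outcome is to hold or stop accrual. It also does not say whether accrual is held while the look takes place. Its decision test concerns dose reductions. A patient who dies or leaves treatment outright need not have had one, so serious toxicity could be seen in the review and still not bear on the stated test.

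The trial gives the 600 mg/day starting dose to adults aged 70 and older because, by its own rationale, evidence on tolerability at that age is limited. If unacceptable toxicity were frequent, whether and when enrolment paused would depend wholly on judgement. The chance that the plan as written would react to a given true rate cannot be calculated.

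**Working it through.** **1. Where a rule could be.**
- Section 5.4 and the tables in Section 6.2 contain hold, reduction and discontinuation rules for individual patients. None acts on the study.
- Sections 13.1 to 13.4 and the synopsis contain one look and no boundary, threshold or error rate.
- Section 7.3.6 contains periodic review and a vote, without a trigger.
- Appendix I lists the DSMC charter as a supplement outside the protocol. The charter and the institutional monitoring plan were not available to us. The design schema figure is not shown; its visible footnote mentions only the interim safety analysis.

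**2. The plan's own safety figures.** Section 13.2 says: "Further a sample size of 40 will allow us to see a toxicity with a true rate equal to 0.05 in 87 out of 100" (repetitions of the study).
- Check: 1 − 0.95^40 = 0.871, which agrees.
- The exact 95% limits for 20/40 are 0.338 to 0.662, which agree with the stated 0.34 and 0.66.
- These figures are correct. They describe detection and precision at the end of the trial, not when to pause.
- At the look, the same detection probability is 1 − 0.95^20 = 0.64.

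**3. Timing**, assuming uniform accrual of 40 patients over the 24 months in the synopsis.
- Rate: 40/24 = 1.67 per month.
- The 20th patient enters at 20/1.67 = 12.0 months. One 28-day cycle adds 28/30.4 = 0.92 months, so the look falls at about month 12.9.
- Enrolled by then: 1.67 × 12.9 = 21.5. Still to come: 40 − 21.5 = 18.5.
- Between six-monthly DSMC reports: 1.67 × 6 = 10 patients.

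**4. What a trigger could deliver (illustration only).** The reference rate p0 = 7.5% is an assumption. It borrows the proportion who discontinued for adverse events on ribociclib plus letrozole in the trial cited in Section 2.4.1.

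Boundary: at each n from 2 to 40, take the smallest k ≥ 2 with P(X ≥ k | n, 0.075) ≤ 0.04.
- Example at n = 10: P(X ≥ 2) = 1 − 0.925^10 − 10 × 0.075 × 0.925^9 = 0.170, too large.
- Subtracting P(X = 2) = 45 × 0.075² × 0.925^8 = 0.136 gives P(X ≥ 3) = 0.034, so k = 3.

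| Patients | Refer at |
|---|---|
| up to 4 | 2 events |
| 5–10 | 3 |
| 11–17 | 4 |
| 18–25 | 5 |
| 26–34 | 6 |
| 35–40 | 7 |

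Exact probability of triggering by patient 40, with each outcome known before the next enrolment:

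| True rate | P(trigger) |
|---|---|
| 7.5% | 0.097 |
| 15% | 0.533 |
| 20% | 0.802 |
| 25% | 0.938 |
| 30% | 0.986 |

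**5. Effect of delayed outcomes.** Under the same immediate-outcome assumption, a true 25% rate triggers after 14.7 patients on average. A simulation with planned accrual, and event times spread evenly over a window after start of treatment, gives the mean number enrolled at the trigger (40 if it never triggers) at a true 25%:

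| Event window | Mean enrolled |
|---|---|
| 1 month | about 15 |
| 3 months | about 19 |
| 6 months | about 23 |
| 12 months | about 30 |

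The early protection therefore depends on a short event window.

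**The case against.** The strongest reply is that oversight exists and is layered. The PMT is recommended to meet at least monthly and to consider further enrolment. The DSMC receives six-monthly reports covering all adverse events and votes on the study. Under Section 7.1.3.2.1, serious adverse events and deaths within 30 days of treatment reach the Coordinating Center within 24 hours. Section 7.1.3.3.1 sends qualifying events on to the IRB and DSMC. The Section 13.3 review also covers more than dose reductions. All of this stands. A reader might infer that the second half of the trial goes unreviewed, or that accrual cannot be stopped. The documents do not support either inference; what is absent is a numerical trigger.

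A second reply is that this is a 40-patient, single-arm estimation study described as IND-exempt, with detailed patient-level dose rules, so a formal boundary is optional. That also stands: nothing in the documents shows a boundary to be required. But Section 7.3.3 speaks of stopping rules as though they exist, and that cannot stay as it is.

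A third reply concerns the illustration. The 7.5% is discontinuation due to adverse events, not limited to ribociclib-attributed events, in a trial with median age 62. It has no stated window. The true rates tried are assumptions. The table shows feasibility and does not supply this trial's rule.

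**Conclusion.** The point holds as an undefined reference and a missing numerical trigger. Section 7.3.3 requires stopping rules to be implemented, and the available text defines none. Section 13.3 is a single opinion-based look that lists no pause.

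In size, no event count governs accrual for the roughly 21 to 22 patients enrolled by the look or the 18 to 19 after it. These counts assume uniform accrual at the planned rate. The sample-size and precision figures are correct and unaffected.

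The conclusion is limited to the protocol text. A rule held in the DSMC charter or institutional plan cannot be excluded, but Section 7.3.3 points to neither and assigns implementation to the PMT.

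**What to change.** Reconcile 7.3.3 with 13.3. The preferred change is to add to 13.3, and cite from 7.3.3, a count-based trigger over patients 1 to 40 at which the PMT holds new registrations and refers to the DSMC. It should state:
- the event: unacceptable toxicity attributed to ribociclib at the possible-or-above level already used in 13.1.4;
- a fixed early window, for example cycle 1 or the first cycles;
- the reference rate and boundary table;
- operating characteristics calculated with accrual continuing during the window.

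The sponsor and clinical team set the event, window and reference rate. The trigger governs registration and referral only and changes no dose or patient-level rule.

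The cost is a paragraph and a small table, using the existing PMT and DSMC. With a boundary like the illustration, the downside is about a 10% chance of one unneeded pause and review when the true rate equals the reference rate.

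If the sponsor intends monitoring by judgement alone, remove the stopping-rule reference from 7.3.3 and say so.
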